# Report follow-up SAE information within 24 hours of becoming aware to:

[contact].

#### 7.3.5.3 Pregnancy

Pregnancies occurring in subjects enrolled in a study or in a female partner of a male study participant must be reported and followed to outcome. If a female subject inadvertently becomes pregnant while on study treatment, the subject will immediately be removed from the study. Any pregnancies of female study subjects and partners of male study subject that occur within 120 days following the last dose of study treatment must be captured in the eCRF.

The Investigator should complete the initial Pregnancy Report Form and forward it to the Sponsor (or designee) within 24 hours of becoming aware of the pregnancy as described in Section 7.3.5.1 of the protocol. If there is an associated serious outcome, then both the initial Pregnancy Report Form and SAE Report Form should be completed.

The site will follow-up with the subject at least monthly and document the subject's status until the pregnancy has been completed or terminated. The Investigator will make every effort to obtain permission to follow the outcome of the pregnancy and report the condition of the fetus or newborn to the Sponsor. The Pregnancy Report Form should be updated and submitted to the

Sponsor within 24 hours of becoming aware of the pregnancy outcome. If an SAE occurred, then the SAE Report Form must be completed and submitted as well.

In the event the pregnancy outcome occurs following the end of the study and database lock, the Investigator will report the pregnancy outcome to the Sponsor (or designee) within 24 hours after the outcome of the pregnancy is known to the Investigator in accordance with the procedure for reporting SAEs (Section 7.3.5.1).

Pregnancy alone is not regarded as an AE unless there is a possibility that the study drug may have interfered with the effectiveness of a contraceptive medication. Elective abortions without complications should not be considered AEs unless they were therapeutic abortions but should be reported to the Sponsor. Hospitalization for normal delivery of a healthy newborn should not be considered an SAE. Pregnancy is not considered an SAE unless there is an associated serious outcome. Spontaneous abortions should always be reported as SAEs.

Any SAE that occurs during pregnancy must be recorded on the SAE Report Form (e.g., maternal serious complications, therapeutic abortion, ectopic pregnancy, stillbirth, neonatal death, congenital anomaly, birth defect) and reported within 24 hours in accordance with the procedure for reporting SAEs.

The Pregnancy Report Form and any related SAE Report Forms must be reported to the Sponsor as outlined for SAEs in Section 7.3.5.2.

#### 7.3.5.4 Regulatory Reporting

Kadmon Pharmacovigilance (or designee) will submit SAEs that meet the criteria for expedited reporting to the Regulatory Authorities in accordance with local regulations governing safety reporting. Reporting of SAEs by the Investigator to his or her IRB/IEC will be done in accordance with the standard operating procedures and policies of the IRB/IEC. Adequate documentation must be maintained showing that the IRB/IEC was properly notified.

### 7.4 Other Safety Considerations

#### 7.4.1 Laboratory Data

All laboratory data obtained during the course of the study should be reviewed. Any abnormal value that leads to a change in subject management (e.g., dose reduction or delay, requirement for additional medication or monitoring) or is considered to be of clinical significance by the

Investigator should be reported as an AE and/or SAE as appropriate, unless this value is consistent with the subject's present disease state or is consistent with values obtained before entry into the study.

Laboratory results will be classified using the CTCAE v4.03.

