#### 3 INVESTIGATIONAL PLAN

# 3.1 Study Design

This will be a Phase 2, open-label, extended treatment and follow-up study in subjects with cGVHD who have been previously treated with belumosudil in Study KD025-208 (see Section 1.4.1) or in Study KD025-213 (see Section 1.4.2).

Subjects will not be screened.

Subjects who have signed the ICF will be enrolled in Study KD025-217 if they have met any of the following conditions:

- Actively receiving belumosudil in Study KD025-208 or in Study KD025-213 (excluding adults in the Companion Study and excluding adolescents enrolled under KD025-213 Amendment 2 [01June 2020])
- Is in long-term follow-up (LFTU) on Study KD025-208 or Study KD025-213.
   Long-term follow-up will be defined as the period after ending treatment with belumosudil and until an FFS event occurs.
- Adult enrolled in the Companion Study as specified in Study KD025-213 Amendment 2
   (01 June 2020) and received at least 6 months of treatment or is in LTFU

After signing the ICF, at Baseline, subjects will undergo efficacy assessments by Clinician-reported Global cGVHD Activity Assessment, response assessment, pulmonary function tests (PFTs), Lee Symptom Scale (LSS) score, and documentation of corticosteroid dosage and/or other therapies for cGVHD.

Subjects will undergo safety assessments including symptom-directed PE, vital signs, weight, height, KPS, hematology and clinical chemistry laboratory testing, pregnancy testing, 12lead ECG, documenting concomitant medications, and monitoring for AEs. Subjects will continue on their same dosing regimen they received in Study KD025-208 or Study KD025-213: belumosudil 200 mg QD, 200 mg BID, or 400 mg QD. If the Investigator reduced the subject's dose of belumosudil in either Study KD025-208 or Study KD025-213, the subject will continue to receive that same reduced dose treatment with belumosudil throughout Study KD025-217 or until the AE that led to the temporary dose reduction has resolved, in which case the dose treatment can resume at the original dose at the discretion of the Investigator. Subjects will be

given a study drug diary to record daily dosing. Subjects may be administered the first dose either in the clinic or self-administered at home.

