### 5.10 Dose Modification Guidelines

Any clinically significant toxicity will necessitate consideration of either a pause or cessation of therapy. Guidelines for management of treatment-emergent toxicities in subjects receiving belumosudil are outlined in Table 5. When dose reduction is necessary, the dose should be decreased as shown in Table 6.

Table 5. Guidelines for the Management of TEAEs with Belumosudil Treatment

Toxicity	Recommended Action		
Grade 4 organ toxicities considered at least possibly related to belumosudil	Discontinue belumosudil		
Grade ≥ 3 LFTs (AST, ALT or total bilirubin) regardless of attribution to belumosudil	
 
Hold belumosudil dosing until resolution to Grade 1 or below levels
 
Consider resuming belumosudil. If resuming, then resume at 1 dose decrement
 
If toxicity recurs, discontinue belumosudil
 
		
Other Grade ≥3 clinically significant toxicities considered at least possibly related to belumosudil	Hold belumosudil dosing until toxicity has resolved to Grade 1 or below then consider resuming belumosudil. If resuming, then resume at 1 dose decrement     If toxicity recurs, hold dose as above then consider resuming belumosudil at one dose decrement		

ALT = alanine aminotransferase; AST = aspartate aminotransferase; eCRF = electronic case report form; LFT = liver function test; TEAE = treatment-emergent adverse event

Dose interruption for up to 14 days for toxicity management is permitted. Subjects requiring pauses of more than 14 days will be discontinued from the study unless approved by the medical monitor.

Table 6. Belumosudil Dose Decrements

Belumosudil Dose	Dose Reduction	
400 mg QD	200 mg QD	
200 mg BID	200 mg QD	
200 mg QD	200 mg QOD	

BID = twice daily; QD = once daily; QOD = once every other day

If the reduced dose of belumosudil is tolerated for 1 month, the dose may be escalated to the previous dose.

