#### 6.2.2 Baseline Visit

Subjects will be evaluated to determine if they meet all inclusion/exclusion criteria. Those signing the ICF will be enrolled in the study.

Note: If the subject was in LTFU in Study KD025-208 or in Study KD025-213, the subject will only have LTFU assessments performed once approximately every 3 months (Section 6.2.5).

Belumosudil will be administered as follows:

- Subject receives same dose of belumosudil as assigned in Study KD025-208 or in Study KD025-213, as appropriate. The first dose may be taken at home or in the clinic.
- Dispense a study drug diary to the subject

The following data will need to be captured from Study KD025-208 or Study KD025-213:

- The dosing group to which the subject was assigned or randomized
- Clinician-reported Global cGVHD Activity Assessment from Day 1
- Any ongoing AEs

The following efficacy assessments will be performed:

Clinician-reported Global cGVHD Activity Assessment

- Response assessment. (Note: all responses will be assessed with respect to Cycle 1 Day 1 of Study KD025-208 or Study KD025-213.)
- PFT (for subjects with lung cGVHD or when lung cGVHD is suspected)
- LSS
- Use of corticosteroid dosage
- Use of other cGVHD therapies

The following safety assessments will be performed:

- Symptom-directed PE
- Vital signs
- Weight and height
- KPS
- Hematology lab testing
- Clinical chemistry lab testing
- 12-lead ECG
- Urine pregnancy test (any positive results will be confirmed with serum testing)
- Use of concomitant medications
- AEs

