3.1.5 Baseline

Baseline value for efficacy analyses is defined as the valid and last non-missing value obtained within 28 days prior to subject receiving the first study medication in parent study KD025-208/KD025-213.

Baseline value for safety analyses is defined as the "Baseline" visit from KD025-217.

Baseline can be the day before the first study medication or on the same day as the first study medication if a pre-dose assessment is available. Subjects without data on a parameter before the first study medication will have a missing baseline for this parameter.

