3.8.1 Adverse Events

AEs will be coded using the MedDRA dictionary (Version 24.1 or higher). Treatment-emergent AEs (TEAEs) are any AEs occurring or worsening in severity after the first administration of study medication until 28 days after EOT. All AEs will undergo 4 sets of ratings by Investigator as follows:

- Serious vs. non-serious [based on seriousness criteria of death, life threatening, hospitalization – initial or prolonged, IME, disability or permanent damage, congenital anomaly or birth defects, and required intervention]
- Grades using the 5-point Common Terminology Criteria for Adverse Events (CTCAE 4.03) scale (mild, moderate, severe, life-threatening, or death)
- Causality assessment with respect to study drug classified as either: related (definitely related, related, probably related, and possibly related) or not related (unlikely related, not related).
- The relationship of AEs to cGVHD or the underlying disease

Kadmon Corporation

Page 20 of 26

The number (N) and percentage (%) of patients who experienced at least one TEAE will be summarized by dose group, including tabulation by:

- System Organ Class (SOC) and PT within each SOC in decreasing total frequency
- · Decreasing frequency of PT
- Maximum severity
- Relationship to study drug

These analyses will be repeated for serious TEAEs, events leading to dose modification, events leading to study drug discontinuation, events related to study drug and events related to cGVHD or the underlying disease.

Subject listings will be provided for AEs, SAEs, AEs resulting in study drug discontinuation and deaths. Time to onset and duration of AEs will be included in listings, along with action taken and outcome.

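### Protocol 7.4.1 lets a laboratory value that prompts a belumosudil hold or reduction go unrecorded as an AE when it resembles on-drug values from the parent study

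*Protocol*

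**What the plan says.** Protocol 7.4.1 sets the reporting trigger: "Any abnormal value that leads to a change in subject management (e.g., dose reduction or delay, requirement for additional medication or monitoring" are its examples, and clinical significance in the investigator's view is a second trigger. Such a value is to be reported as an AE or SAE. The same sentence then makes two exceptions. One is for values in keeping with the current disease state. The other is for a value that "or is consistent with values obtained before entry into the study".

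On who enters, protocol 3.1 lists subjects "Actively receiving belumosudil in Study KD025-208 or in Study KD025-213", adults from the Companion Study with at least 6 months of treatment, and subjects in long-term follow-up. For those who arrive already in follow-up, protocol 6.2.2 says that "the subject will only have LTFU assessments performed once approximately every 3 months".

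Protocol 7.2 treats a laboratory result that is worse than at Baseline as an AE. Protocol 6.2.2 and footnote b of the Schedule of Assessments bring AEs still ongoing from the parent study into the KD025-217 record at Baseline.

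SAP 3.8.1 tabulates treatment-emergent AEs by severity and relationship, and adds: "These analyses will be repeated for serious TEAEs, events leading to dose modification", with events leading to drug discontinuation and drug-related events in the same list. SAP 3.1.5 places the safety baseline at the KD025-217 Baseline visit.

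**The concern.** An exception for values seen before study entry is ordinary in a first-exposure trial, where those values are drug-free and describe the subject's own background. In an extension the same words reach back into a period of treatment. Nothing in 7.4.1 restricts them to values from before the first dose in the parent study.

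The stated objective is long-term safety. A laboratory abnormality that appears on drug, settles and returns, or that persists until someone decides to change the dose, is the sort of harm that such a study is placed to describe. If it leaves no AE record, it cannot enter the tables of related events or of events leading to dose modification. No causality rating is then made, and the 7.4.2 requirement to follow treatment-emergent AEs to resolution or stability has nothing to attach to.

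**Working it through.** The documents state no figure on this point, so the check sets the rules side by side. Baseline in 7.2 is read as the KD025-217 Baseline visit, which is how the protocol uses the word.

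Take a continuing subject whose laboratory value leads to a hold or reduction, so that the 7.4.1 trigger is met, and ask what each rule does.

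| Situation | 7.2 (worse than Baseline) | 7.4.1 (pre-entry exception) | Carried forward at Baseline (6.2.2) | Result |
|---|---|---|---|---|
| Worse than any earlier value | AE | Does not apply | Not needed | AE recorded |
| AE in the parent study, still ongoing, unworsened | No worsening | Exempt | Yes | A record exists |
| Abnormal on drug in the parent study, resolved by entry, recurs at a similar level | AE | Exempt | No, since not ongoing | Rules conflict |
| Chronic and unworsened, not held as an ongoing AE | No worsening | Exempt | No | No AE required |

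The third row can arise under the protocol's own provisions. Sections 3.1 and 5.3 allow a subject whose dose was reduced in the parent study to return to the original dose after the AE resolves. If the abnormality then reappears, it matches a pre-entry value. Appendix G uses reappearance on rechallenge as a criterion for its highest causality category, so the exception can remove a record that is informative about causality.

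Next, whether other planned outputs fill the gap.

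- Protocol 9.9 and SAP 3.8.2 report Grade 3 or higher incidence, worst grade, grade shifts and a listing of Grade 3 or higher results from the laboratory data. These do not depend on AE forms, so the value remains visible.
- That listing is not specified to carry causality, action taken or outcome. SAP 3.8.1 puts action and outcome in the AE listings.
- The listing leaves out Grade 1 and 2 values. Protocol 5.10 lets any clinically significant toxicity prompt consideration of a pause or cessation.
- Shift tables start from the KD025-217 Baseline, which is on drug for continuing subjects. A chronic abnormality can therefore appear as no shift.
- Discontinuations have a second route: protocol 15.4 puts dates and reasons for stopping on the eCRF, and SAP 3.3 summarises the primary reason. Holds and reductions are not included in that summary.

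Size. The documents give no count of values that would fall under the exception. Parent-study rates can only show that such abnormalities occur, and they do not agree. Scaling each to the planned 70 or so subjects, for illustration:

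- KD025-208 (Table 2), Grade 3 or higher GGT increase from any cause: 4/54 = 7.4%, and 70 × 4/54 = 5.2.
- KD025-208 (Table 2), drug-related Grade 3 or higher ALT increase, and likewise AST: 2/54 = 3.7%, and 70 × 2/54 = 2.6.
- KD025-213 (Table 4), drug-related Grade 3 or higher GGT increase: 2/132 = 1.5%, and 70 × 2/132 = 1.1.
- KD025-213 (Table 4), drug-related Grade 3 or higher ALT or AST: neither appears in a list of terms above 1%, so each is at most 1/132 = 0.8%, and 70 × 1/132 = 0.5.

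None of these is a rate of exempted dose changes. They count events that were recorded as AEs in the parent studies. The 70 also includes subjects already in follow-up, who have no scheduled laboratory tests here.

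**The case against.** The strongest reply is that most cases are caught elsewhere. Ongoing parent-study AEs are brought in at Baseline, worsening from Baseline is an AE under 7.2, and 7.3.4 requires a new entry when the grade of an AE rises. A value that was tolerated and later forces a hold will often have worsened. This stands, and it confines the gap to the last two rows of the table.

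A reader might infer that laboratory toxicity as a whole will be under-reported. The documents do not support that. The laboratory tables and the Grade 3 or higher listing are independent of AE forms, and reasons for discontinuation are captured separately.

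A reader might also infer a contradiction with Table 5 in protocol 5.10, which calls for a hold for Grade 3 or higher AST, ALT or total bilirubin "regardless of attribution to belumosudil", while 7.4.1 exempts values in keeping with the disease state. There is no contradiction: Table 5 governs dosing and 7.4.1 governs recording. Recording such values anyway, with cGVHD named as a possible cause, is a sensible preference rather than the correction of an error.

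Finally, pre-entry values are not all on-drug values. They also include those from before the first parent-study dose. Judging whether a value is consistent with earlier ones is left to the investigator, so the exception is not automatic. Both points limit how often it will be used. Neither restricts the reference period.

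**Conclusion.** The point holds in a limited form. Followed literally, 7.4.1 allows an on-drug laboratory abnormality that leads to a hold or reduction to go without an AE record in two situations: recurrence at a similar level after resolution, and a chronic unworsened abnormality not carried forward as ongoing. In the first, 7.4.1 and 7.2 give opposite answers. The loss is of the AE record, its causality rating and its place in the SAP tables of related and dose-modifying events, not of the laboratory value.

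The number affected cannot be derived. It would be tempting to read the KD025-208 rates as about 5 subjects for GGT and about 3 for ALT or AST. The larger parent study gives about 1 for drug-related GGT and at most about 0.5 each for ALT and AST by the same arithmetic, and neither set measures what the exception removes.

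The conclusion rests on two assumptions: that entry into the study means entry into KD025-217, and that sites apply the exception as written. The change is worth making because it removes a source of bias from the AE tables at little cost.

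**What to change.** Amend protocol 7.4.1 in three respects. The change affects recording only and leaves every dosing rule as it is.

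1. Define the reference as values obtained before the first dose of belumosudil in KD025-208 or KD025-213.
2. State that any laboratory value leading to a hold, reduction or discontinuation of belumosudil is recorded as an AE whatever the earlier values were, with cGVHD noted as an alternative cause where relevant.
3. Reconcile 7.4.1 with 7.2, so that a result worse than at Baseline is handled in the same way under both.

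The cost is a few lines of protocol text, a note to sites and a few more AE records. No SAP table needs to change, since those in 3.8.1 would take up the added records as already specified.

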# 7.4.2 Follow-Up of Adverse Events

All SAEs and TEAEs (including clinically significant abnormal laboratory values that meet these criteria) will be followed until either resolution of the event or determination by the Investigator that the event has become stable or irreversible. The status of all other continuing AEs will be documented as of 28 days after last dose of study drug.

# **8 STUDY STOPPING RULES**

There are no stopping rules for this study.

#### 9 STATISTICAL CONSIDERATIONS

### 9.1 Hypothesis

This will be a long-term follow-up study of the efficacy and safety of subjects treated with belumosudil in Study KD025-208 and Study KD025-213. No formal hypothesis will be used.

#### 9.2 Sample Size and Power Calculation

No formal power calculation will be performed to determine the study sample size.

#### 9.3 Analysis Populations

The populations for efficacy and safety analyses will be the Full Analysis Set consisting of all subjects enrolled in the study.

There are 3 treatment groups for this study: belumosudil 200 mg QD, 200 mg BID, and 400 mg QD. Each subject's treatment group is determined by their originally assigned dosing cohort (Study KD025-208) or randomized arm (Study KD025-213).

## 9.4 Subgroup Analyses

No subgroup analysis will be conducted.

#### 9.5 Data Analysis

All pre-specified analyses will be described in a Statistical Analysis Plan.

#### 9.6 Interim Analysis

An interim analysis will be performed when all subjects have completed at least 3 years of treatment with belumosudil or withdrew earlier (not inclusive of the companion study subjects).

### 9.7 Efficacy Analyses

The follow-up efficacy endpoints in this study are described in Section 6.3.

#### 9.8 Exploratory Analyses

No exploratory analyses will be conducted.

### 9.9 Safety Analyses

Safety analyses will be performed on all subjects who receive at least one dose of belumosudil.

Adverse events will be coded using the Medical Dictionary of Regulatory Activities (MedDRA) (Version 24.0 or greater). The number and percentages of subjects experiencing TEAEs will be tabulated by System Organ Class and Preferred Term (PT). The number of events by PT will also be summarized. Tabulation by maximum severity and relationship to treatment will also be included by treatment group.

Summary subject listing will be provided for SAEs, AEs resulting in study discontinuation, and deaths.

Adverse events, SAEs, related AEs, related SAEs, Grade  $\geq$  3 AEs, related Grade  $\geq$  3 AEs, and AEs leading to withdrawal and treatment discontinuation, and deaths will be summarized.

Laboratory results will be summarized by treatment group, incidence of laboratory abnormalities, and worst on-study grade during the treatment period will be summarized. The incidence of Grade  $\geq$  3 laboratory abnormalities under treatment and shifts in toxicity grading from Baseline to highest grade post-baseline will be displayed.

Vital sign measurements and ECGs will be summarized by treatment group at each scheduled time point using descriptive statistics and included in data listings.

